do not show up to the first scheduled clinician visit will be considered enrolled and included in the primary analysis.

--Power Calculations--

For the following power calculations, we used an adjusted Type I error of 0.025 to account for two comparisons: 1) clinic-level nudges versus usual care, and 2) intensification for high-risk patients versus no intensification within practices where clinic-level nudges are provided. Based on retrospective data from our health systems, we will have 85% power to detect a 7-percentage point difference in the flu vaccine completion rate for comparison #1. This calculation assumed N=48 participating clinics across the two sites, an average cluster size of n=1385 patients, and an intracluster correlation (ICC) of 0.02. For comparison #2, we will have at least 99% power to detect a 2-percentage point difference even if the rate of vaccination in the high-risk group is 50%, the most conservative rate with respect to power. This calculation assumed 1:1 individual-level randomization of n=1000 high-risk patients within each of N=32 clinics that will be randomized to receive clinic-level nudges. These power calculations used combined retrospective data from Penn and UW to estimate the average number of patients per clinic and the number of high-risk patients who will be randomized. We expect to have greater power for both comparisons at the replication site which comprises more clinics and patients.

--Statistical Analysis--

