BE IMMUNE: Behavioral Economics to IMprove and Motivate vaccination Using Nudges through the EHR

University of Pennsylvania

[name]

[name]

[name]

NCT#06057727

Statistical Analysis Plan

01/07/2025

Objectives

Our primary objective is to test the effectiveness of multicomponent, personalized EHR-based nudges to both clinicians and patients for increasing flu vaccination completion among eligible primary care patients.

Relevant Study Design Details

Randomization

Primary care clinics will be randomized 2:1 to either a nudge intervention or usual care arm using covariate-constrained randomization, stratified by health system (Penn, UW). For the clinic level randomization, the covariate-constrained randomization will aim to balance the distribution of clinician panel baseline flu vaccination completion rate, panel size, and panel risk. Panel size is defined as the number of patient visits from September 1, 2022 through February 28, 2023. Panel risk is defined as the proportion of a clinician's patients who meet at least one of the following criteria: age \geq 70 years, Non-Hispanic Black race, residence in lower income communities (lowest quartile according to zip code), or no documented history of flu vaccine in the year prior. Second, patients who have an eligible appointment at an intervention clinic and are identified as high-risk for not completing a flu vaccination will be further randomized using a 1:1 ratio at the patient level—stratified by clinic—to receive either an additional, intensification nudge (bi-directional texting) or the standard nudge intervention (standard text messaging).

Blinding

All investigators, statisticians, and analysts will be blinded during the randomization, intervention, and analysis phases. They will be unblinded at the end of the study analyses, after all outcomes have been obtained.

Outcomes

The primary outcome is flu vaccination completion during the first eligible primary care visit.

Secondary outcomes are flu vaccination completion within 3 months of the first eligible primary care visit and flu vaccination ordering. These patient-level outcomes will be coded as a 1 to indicate completion (or signed order) and 0 to indicate non-completion (or unsigned/cancelled order).

Statistical Analysis

The primary analysis for all primary and secondary outcomes will follow the intent-to-treat principle.

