We will test each of the four linear contrasts of the parameters estimated from the GEE model. We will use a Bonferroni correction for the first two contrasts, aligning with how the study was powered (i.e., two-sided significance level of 0.025 for the first two contrasts). We will consider contrasts 3 and 4 as exploratory, and thus we will not correct the corresponding p-values for multiple testing. Results will be reported on the odds ratio scale, including 95% confidence intervals. Confidence intervals for contrasts 1 and 2 will incorporate the Bonferroni correction used for the two tests.

Sensitivity Analyses to Evaluate Model Specifications

As a sensitivity analysis, we will restrict the data to high-risk patients at active clinics and estimate the main effect of intensive vs standard text messaging, specifying an exchangeable working

correlation within clinics. As another sensitivity analysis, we will use an exchangeable working correlation at the clinic level after duplicating each clinic's data, assigning one 1 and one -1 for patients without an individual-level assignment, and removing the record for each high-risk patient an intervention clinic corresponding to the opposite of the individual-level randomized assignment that was received. Duplicated clinics will be treated as independent while observations within clinic will be treated as exchangeable. In this way, duplicated records will be treated as independent. Using this approach, we will re-test the main effect of A_1 , i.e., $2\beta_1$, to evaluate sensitivity to specification of the working correlation. We will use a t-distribution with degrees of freedom equal to the number of clinics (47) minus the number of mean model parameters to construct a confidence interval for $2\beta_1$. If the interval does not include 0 (log odds ratio scale) we will reject the null and conclude there is a significant effect of clinic nudges compared to usual care.

Sensitivity Analyses to Evaluate Protocol Deviations

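### Holm in place of plain Bonferroni for the two corrected contrasts would recover unused power at the same 5% familywise error: a cheap improvement, not an error in the plan

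*SAP*

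**What the plan says.** The SAP, under Analytical Plan for Primary and Secondary Outcomes, defines four contrasts from one GEE model. For the clinic-level nudge effect (contrast 1) and the intensive-versus-standard texting effect (contrast 2) it states: "We will use a Bonferroni correction for the first two contrasts". It gives consistency with the power calculation as its reason and spells the rule out as a "two-sided significance level of 0.025 for the first two contrasts". Contrasts 3 and 4 are exploratory and uncorrected. The confidence intervals for contrasts 1 and 2 carry the same correction, which makes them 97.5% intervals. The same modelling approach serves the primary and the secondary outcome.

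The protocol's Power Calculations (section 9) agree: "we used an adjusted Type I error of 0.025 to account for two comparisons". For the clinic comparison they say "we will have 85% power to detect a 7-percentage point difference in the flu vaccine completion rate for comparison #1", with these inputs: "This calculation assumed N=48 participating clinics across the two sites, an average cluster size of n=1385 patients, and an intracluster correlation (ICC) of 0.02". For the texting comparison they say "we will have at least 99% power to detect a 2-percentage point difference even if the rate of vaccination in the high-risk group is 50" percent.

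Neither document mentions Holm, a fixed testing order, or passing alpha from one contrast to the other.

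**The concern.** With two tests, Bonferroni holds each at 0.025 whatever happens to the other. Holm starts at the same place, with the smaller p-value tested at 0.025. If that test rejects, the other p-value is tested at 0.05. It needs no further assumption about the data, no more patients and no more clinics.

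This matters most for contrast 1. Its precision is limited by the number of clinics, because at an intracluster correlation of 0.02 and about 1,385 patients per clinic, extra patients add little. The protocol's 85% assumed 48 clinics. The SAP gives 45 in the main analysis section and 47 in the sensitivity analysis of the working correlation. The SAP also reports that Penn intervention clinics had no pended orders in the first six weeks. Keeping those patients as assigned is sound intention-to-treat practice, but it may dilute the contrast.

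**Working it through.** **Inputs.** From the protocol's Power Calculations: 48 clinics, 1,385 patients per clinic, ICC 0.02, a 7-point difference, and 32 clinics × 1,000 high-risk patients randomized 1:1 for comparison #2. From the SAP: 2:1 clinic allocation ("Primary care clinics will be randomized 2:1 to either a nudge intervention or usual care arm"), 45 clinics, two-sided 0.025. Assumed: a control rate of 35% (none is given; varied below), independent test statistics, and two-proportion approximations in place of the GEE. Write P1(a) and P2(a) for the power of each contrast at two-sided level a. Critical values are 2.241 at 0.025 and 1.960 at 0.05.

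**1. Reproduce the stated 85%.** Design effect = 1 + 1,384 × 0.02 = 28.68, so a clinic is worth 1,385 / 28.68 = 48.29 independent patients. With 16 control and 32 nudge clinics the effective sizes are 772.7 and 1,545.3.

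SE = √(0.35 × 0.65 / 772.7 + 0.42 × 0.58 / 1,545.3) = 0.02126, and 0.07 / 0.02126 = 3.292.

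P1(0.025) = Φ(3.292 − 2.241) = 85.3%. The stated figure reproduces (84.6% with a pooled variance under the null).

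**2. Contrast 1 with 45 clinics (15 and 30).** Effective sizes are 724.4 and 1,448.7, SE = 0.02196, ratio = 3.188.

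- P1(0.025) = Φ(0.947) = 0.8280
- P1(0.05) = Φ(1.228) = 0.8902

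**3. Contrast 2.** With 32,000 / 2 = 16,000 per arm and 50% versus 52%, the SE is 0.00559. P2(0.025) = 0.9094 and P2(0.05) = 0.9473. The protocol states at least 99%, which this literal reading does not reproduce. Taking 1,000 as per arm per clinic gives 99.8%. Both values are carried forward.

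**4. Familywise error under Holm.** If both nulls are true, a false rejection needs the smaller p-value to be at or below 0.025, which has probability at most 0.025 + 0.025 = 0.05. If only one null is true, rejecting it needs its p-value to be at or below 0.05. Neither step uses independence. With independent tests and both nulls true, both procedures give 1 − 0.975² = 0.0494.

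**5. Power under Holm.**

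Contrast 1: P2(0.025) × P1(0.05) + [1 − P2(0.025)] × P1(0.025)

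- 45 clinics: 0.9094 × 0.8902 + 0.0906 × 0.8280 = 88.5%, up from 82.8%
- 48 clinics: 0.9094 × 0.9086 + 0.0906 × 0.8533 = 90.4%, up from 85.3%

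Contrast 2, by the same formula with the roles exchanged (45 clinics): 0.8280 × 0.9473 + 0.1720 × 0.9094 = 94.1%, up from 90.9%.

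At the protocol's own stated powers of 85% and 99%, contrast 1 rises to 90.6% and contrast 2 to 99.5%.

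**6. How far the gain depends on the assumptions.** The gain for contrast 1 is P2(0.025) × [P1(0.05) − P1(0.025)]. It cannot be negative, and it shrinks with the power of contrast 2. For 45 clinics and a 35% control rate the bracket is 0.8902 − 0.8280 = 0.0622:

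| Power of contrast 2 at 0.025 | Gain for contrast 1 |
|---|---|
| 90.9% | 5.7 points |
| 30% | 1.9 points |
| 2.5% (contrast 2 null) | 0.2 points |

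By assumed control rate, 45 clinics, contrast 2 at 90.9%:

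| Control rate | Bonferroni power | Gain |
|---|---|---|
| 20% | 92.8% | 2.8 points |
| 30% | 85.4% | 5.0 points |
| 35% | 82.8% | 5.7 points |
| 50% | 80.1% | 6.3 points |
| 60% | 82.7% | 5.7 points |

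Simulation with correlations from −0.5 to 0.6 between the two statistics, starting from 85% for contrast 1 and either 90.9% or 99% for contrast 2, gave a gain of 4.4 to 5.6 points for contrast 1.

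**The case against.** The strongest reply is that nothing here is broken. Bonferroni is valid, was pre-specified, agrees between protocol and SAP, and has a stated reason: it matches the alpha used for power. That stands, and a reader who inferred a mistake in the plan would be wrong. The reason given does not require the choice, though. A sample size set at 0.025 per test remains sufficient under Holm, because Holm never rejects less.

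A reader might also infer that the gain is free and accrues to both contrasts regardless. The documents do not support that. Each contrast gains only when the other is rejected at 0.025, and whether bidirectional texting adds anything to standard texting is exactly what contrast 2 asks. If it adds nothing, contrast 1 gains almost nothing. At the protocol's stated 99%, contrast 2 has little to gain.

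Nor is the change without cost. At present each test and its 97.5% interval always agree. Under Holm, a contrast with p between 0.025 and 0.05 can be declared significant beside an interval that includes an odds ratio of 1. Preferring matched tests and intervals is a legitimate choice.

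Timing also counts. The SAP is dated 01/07/2025 and describes the first six weeks at Penn in the past tense, so patients had already accrued. Moving to a less strict rejection rule at that stage needs a documented rationale.

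**Conclusion.** The point holds as an optional efficiency improvement. Plain Bonferroni on contrasts 1 and 2 gives up power that Holm would recover at the same 5% familywise error under any dependence. In the favourable case of both effects at design values and independent tests, contrast 1 gains about 5.7 points with 45 clinics at an assumed 35% control rate. At that control rate the gain is close to zero if contrast 2 has no effect. For contrast 2, the gain of about 3 points rests on a recomputed power of 90.9% that differs from the protocol's stated figure; at the stated 99% it is about 0.5 points.

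These sizes rest on a control rate that the documents do not state and on two-proportion approximations to the GEE contrasts. That Holm loses no rejections and keeps the error rate rests on neither.

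**What to change.** In a dated SAP amendment made before unblinding, state that:

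- the smaller of the two p-values for contrasts 1 and 2 is tested at 0.025 and, if it is rejected, the other is tested at 0.05;
- the rule is applied within each outcome to which the Bonferroni rule now applies;
- the planned 97.5% intervals are kept as conservative simultaneous intervals, while test decisions follow Holm.

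The cost is a few sentences with a recorded rationale, plus a statement in the report that a second-step rejection may accompany a 97.5% interval that includes an odds ratio of 1. No further patients, clinics or model changes are needed. The documents do not show whether unblinding has taken place. If it has, the Bonferroni rule should stay for this trial.

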The weighted and replicated method is an analytic trick that allows for standard statistical software to be used to fit a single model for statistical estimation and inference regarding multiple effects of interest. Only high-risk patients seen at active intervention clinics are randomized to standard or intensive text messaging. Low-risk patients and all patients seen at control clinics are only exposed to the clinic-level randomized assignment. As a result, they do not have an individual-level randomized assignment in the analytic data set. To fit a single model, we must assign these individuals a value for the individual-level randomization. To do so, we first replicate their row of data and assign one of their records to standard messaging and the other to intensive messaging. However, after replicating these individuals, they will be over-represented in the analytic data set compared to high-risk, intervention clinic patients who received an individual-level randomized assignment and are therefore not replicated. To re-balance the representation in the pseudo-population created by replicating some patient observations, we weight each row by the inverse of the probability of receiving the observed value of the individual-level intervention. That is, patients who were truly randomized to standard or intensive texting will receive a weight of 2 (inverse of $\frac{1}{2}$) while each row of a patient whose record was replicated will receive a weight of 1 (since their intervention “assignments” were deterministic).

Once the replicated data set is created, we will fit the following GEE model to the patient-level binary outcomes using the observation weights mentioned above:

$$\text{logit} (\Pr(Y = 1 | A_1, A_2, X)) = \beta_0 + \beta_1 A_1 + \beta_2 A_1 A_2 + \beta_3^T X, \quad (1)$$

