$$\text{logit} (\Pr(Y = 1 | A_1, A_2, T, X)) = \beta_0 + \beta_1 A_1 + \beta_2 A_1 A_2 + \beta_3 T + \beta_4 A_1 T + \beta_5 A_1 A_2 T + \beta_6^T X, \quad (2)$$

where T is a categorical variable indicating study month. We will use the weighted and replicated approach and an independent working correlation structure. We will first assess whether the effect of text messaging style differs over time. If we do not find evidence of effect heterogeneity for text messaging style, we will drop A_2 from the model and focus only on the effect of pended orders over time using the following model:

$$\text{logit} (\Pr(Y = 1 | A_1, A_2, T, X)) = \beta_0 + \beta_1 A_1 + \beta_2 T + \beta_4 A_1 T + \beta_5^T X, \quad (3)$$

Inference will focus on the interaction effect, β_4 , and we will not use any weighting or replicating to fit this model. We will fit this model using an independent working correlation.

Lastly, we will determine which high-risk intensification subgroups experienced the greatest benefits of the clinic- and individual-level nudges. Using the data set restricted to high-risk individuals, we will fit the following model:

$$\text{logit} (\Pr(Y = 1 | A_1, A_2, Z, X)) = \beta_0 + \beta_1 A_1 + \beta_2 A_1 A_2 + \beta_3 Z + \beta_4 A_1 Z + \beta_5 A_1 A_2 Z + \beta_6^T X, \quad (4)$$

where Z is a single, high-risk criteria. We will fit model (2) separately for each high-risk criteria which will allow us to determine which high-risk intensification subgroups experienced the greatest benefits of the clinic- and individual-level nudges. We will again use the weighted and replicated approach,

duplicating each control arm patient and assigning them a weight of 1 while assigning each intervention clinic patient a weight of 2. We will use an independent working correlation structure.

We now provide details about the interaction effects of interest. First, note that the main effect of A_1 amongst $Z = 1$ is:

$$\begin{aligned}\beta_0 + \beta_1 + \beta_2 A_2 + \beta_3 + \beta_4 + \beta_5 A_2 + \beta_6^T X - (\beta_0 - \beta_1 - \beta_2 A_2 + \beta_3 - \beta_4 - \beta_5 A_2 + \beta_6^T X) \\ = 2\beta_1 + 2\beta_4\end{aligned}$$

Similarly, the main effect of A_1 amongst $Z = 0$ is:

$$\begin{aligned}\beta_0 + \beta_1 + \beta_2 A_2 + \beta_6^T X - (\beta_0 - \beta_1 - \beta_2 A_2 + \beta_6^T X) \\ = 2\beta_1\end{aligned}$$

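### The duplicated-clinic sensitivity analysis does not say whether or how the 2-and-1 weights enter, and fitted unweighted its clinic-nudge contrast is non-zero under the null whenever completion differs by risk group

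*SAP*

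**What the plan says.** The SAP's primary analysis (Analytical Plan for Primary and Secondary Outcomes) gives two rows to every low-risk patient and every control-clinic patient, and one row to each high-risk patient at an intervention clinic. It notes that, once replicated, the former group is out of proportion: "they will be over-represented in the analytic data set compared to high-risk, intervention clinic patients who received an individual-level randomized assignment". The correction is explicit: "patients who were truly randomized to standard or intensive texting will receive a weight of 2", while "each row of a patient whose record was replicated will receive a weight of 1". Model (1) is then fitted "using the observation weights mentioned above".

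Under Sensitivity Analyses to Evaluate Model Specifications, the SAP builds a second data set. Each clinic is duplicated, one copy per texting value, and the surplus row of each randomized patient is taken out: "removing the record for each high-risk patient an intervention clinic corresponding to the opposite of the individual-level randomized assignment that was received". On the correlation it says: "Duplicated clinics will be treated as independent while observations within clinic will be treated as exchangeable". The aim is to re-test 2β1 "to evaluate sensitivity to specification of the working correlation", with a t-based interval and a rule to reject the null if that interval excludes zero. The paragraph neither keeps nor drops the weights.

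Elsewhere, several replicated analyses in the Analytical Plan for Exploratory Analyses restate the weights or the weighted approach. For model (3) the SAP says outright "we will not use any weighting or replicating to fit this model".

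**The concern.** The sensitivity data set has the same row imbalance that the primary analysis needs weights to correct. Without them, high-risk patients are under-represented in intervention clinics but not in control clinics. If the two risk groups complete at different rates, the arms then differ in case mix, and 2β1 picks up that difference even when the nudges do nothing. Model (1) requires only clinic-level covariates. These cannot undo a shift created inside every intervention clinic, because the arm coefficient absorbs it.

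This affects the point estimate, not just its standard error. The SAP relies on GEE estimates being consistent under any working correlation. A case-mix artefact could therefore be read as sensitivity to the correlation structure, or as support for the primary result.

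**Working it through.** **Inputs from the documents.** Protocol section 9, Power Calculations: 48 clinics, 1385 patients per clinic, ICC 0.02, 1000 high-risk patients in each of 32 intervention clinics, 85% power for 7 points at an adjusted Type I error of 0.025. SAP: weights 2 and 1, 1:1 texting randomization, two-sided testing. **Assumed:** completion rates by risk group, which the documents do not give (50% for high-risk patients is only a conservative power value).

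**Planned power for the contrast being re-tested.** Design effect = 1 + 1384 × 0.02 = 28.68. Effective control size = 16 × 1385 / 28.68 ≈ 773, with twice that in the nudge arm. At two-sided 0.025, power for 7 points is 84.99% at a control rate of 34% and 84.9% at 58%, with a minimum of 82.6% near 46%. The stated 85% is reproduced for plausible control rates. No figure is stated for the sensitivity analysis.

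**Row shares without weights.** An intervention clinic contributes 1000 high-risk rows and 2 × 385 = 770 low-risk rows.
- High-risk share of rows, intervention: 1000/1770 = 56.5%.
- High-risk share, control: 1000/1385 = 72.2%.
- Difference: 0.157.

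**Null difference, unweighted.** Bias = 0.157 × (pL − pH), where pL and pH are low- and high-risk completion.

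| Assumed gap pL − pH | Spurious difference |
|---|---|
| 0 | 0 |
| 5 points | +0.8 points |
| 10 points | +1.6 points |
| 15 points | +2.4 points |
| 20 points | +3.1 points |
| −10 points | −1.6 points |

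For pH = 40% and pL = 55%, the control mean is 0.722 × 40 + 0.278 × 55 = 44.2% and the intervention mean is 0.565 × 40 + 0.435 × 55 = 46.5%, an odds ratio of 1.10 with no effect present. At a 10-point gap the bias is 1.7 points for a high-risk share of 50% or 60%, and 1.3 points for 80%.

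**Simulation under the null** (2000 trials per scenario; 47 clinics assumed split 31:16; 1385 patients per clinic; ICC 0.02; exchangeable logit GEE on duplicated clinics; no clinic covariates). With pH = 50%, unweighted odds ratios were 1.03, 1.065 and 1.14 for gaps of 5, 10 and 20 points. With standard errors clustered on the actual clinic, rejection at nominal 0.05 was 0.05 with no gap, 0.12 at 10 points and 0.31 at 20 points.

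**If the weights are carried over.** All terms in model (1) are constant within a clinic copy, so what matters is each row's effective weight.
- *Weights multiplying the residuals:* the effective weight is proportional to 2 or 1, as intended. Simulated null odds ratios were 0.998 to 1.002.
- *Weights inside the working covariance (W^1/2 R^-1 W^1/2):* the effective weight is w − c√w × Σ√w, with c = ρ/(1 + (m − 1)ρ). A copy has m = 500 + 385 = 885 rows, so c = 0.02/18.68 = 0.00107. Σ√w = 500 × 1.414 + 385 = 1092, and c × Σ√w = 1.169. Low-risk rows get 1 − 1.169 = −0.17; high-risk rows get 2 − 1.414 × 1.169 = +0.35. With rates of 40% and 55%, the implied intervention mean is (173 × 0.40 − 65 × 0.55)/108 ≈ 31% against 44.2% in control, about −13 points. At pL = 60%, pH = 50%, the simulated null odds ratio was 0.70.

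**One row per patient.** An exchangeable GEE on clinic arm alone gave the same 2β1 as the residual-weighted duplicated fit, to below 0.000001.

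**The case against.** The strongest reply is that the weights are implied. The stated purpose is to change only the working correlation, and 2β1 belongs to model (1), which is fitted with weights. The SAP also relies on the weighted approach without restating it when it repeats the primary analyses after excluding the early Penn patients and when it refits by health system. Where it drops weights, for model (3), it says so. This stands: a reader might infer that the planned analysis is certainly biased upward, but the documents do not say the fit is unweighted. It does not close the matter, because the SAP does not say how weights enter an exchangeable fit, and one way of entering them fails badly. That failure belongs to one possible implementation, not to anything the SAP specifies.

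Other replies that stand:
- A reader might take the row removal as a loss of data. It is not. Each high-risk intervention patient keeps one row, as in the primary analysis.
- The covariate list is a minimum, so a patient-level risk term is allowed, though none is specified.
- Direction and size rest on an assumed gap. The high-risk label points upward, but no completion rates by risk group are reported.
- A reader might infer that this check could overturn the primary result. Nothing in the SAP gives it that role, and the primary weights are fully stated.

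**Conclusion.** The concern holds as a gap in specification with consequences for the estimate. Fitted literally, without weights, the re-test of 2β1 is off under the null by about 0.157 times the risk-group gap: +0.8 to +3.1 points for assumed gaps of 5 to 20 points, the largest being nearly half of the 7-point planning difference. The bias is zero if the groups complete equally and reverses if high-risk patients complete more often. With weights, the result is either correct or strongly biased downward, depending on an unstated choice. These sizes assume the protocol's planning share of high-risk patients and, for the covariance calculation, an ICC of 0.02. The fault is the unstated weighting, not the row removal. It should be fixed because this sensitivity analysis carries its own rejection rule.

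**What to change.** For this sensitivity test of contrast 1, drop the duplication. Use one row per patient and fit logit(Pr(Y = 1)) on A1 and X, with no A2 term, no replication and no weights. Use an exchangeable working correlation and robust standard errors clustered on the actual clinic, and keep the t reference based on the number of clinics.

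Texting is randomized 1:1 within clinic, so the A1 coefficient already averages over it. The averaging is on the probability scale rather than the log-odds scale, but for the planning values of 50% and 52% this hardly matters: logit(0.51) = 0.0400, and the mean of logit(0.50) and logit(0.52) is also 0.0400. The fit matches the protocol's comparison #1 (section 9, Statistical Analysis) and uses the same unreplicated, unweighted data as model (3).

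Clustering on the actual clinic also matters separately. If the sandwich estimator treats the two copies as independent clusters, standard errors are too small by about √2, and simulated rejection at nominal 0.05 was about 0.17 even with correct weights.

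If duplication is kept, the SAP should state weights 2 and 1, apply them to the residuals outside the working covariance, and cluster on the actual clinic. Either change costs SAP wording and a small code edit; the preferred one simplifies the code. Neither needs new data or patients.
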